## **8 TREATMENT EXPOSURE AND COMPLIANCE**

The duration of infusion in minutes and volume of infusion in mL will be summarized by treatment group with n, mean, SD, median, minimum and maximum in the Safety and MITT populations. The number and percentage of subjects in each treatment group who received diphenhydramine per protocol, received an NSAID per protocol, had an infusion interruption of > 15 minutes, and did not receive the full infusion will also be summarized in the Safety and MITT populations. If there are a large number of interruptions (10% or more), incomplete infusions, or subjects not receiving the protocol-specified pre-treatment medications, the duration of infusion and volume of infusion summaries may be repeated with subsets based on these dosing parameters. The decision to generate any subset summaries will be made before unblinding the study.

## **9 EFFICACY ANALYSES**

Efficacy analyses (including the primary efficacy analyses) will be performed using the MITT population and based on the treatment to which they were randomly assigned.

### **9.1 Primary Efficacy Analysis – Day 7 Ordinal Scale Status**

The ordinal scale outcomes will be measured daily from Day 1 (Baseline) through Day 14 using the seven-level hierarchical scale with the classifications presented in the table below. The clinical outcomes therein are ordered from the worst clinical outcome to the best clinical outcome in descending order. For each day, subjects will be classified by the worst clinical

January 17, 2019

outcome for which they qualify. The number and percentage of subjects in each treatment group with each classification will be summarized for each day from Day 1 through Day 14, inclusive. For subjects who die prior to Day 7, the score of 7 will be carried forward through Day 14. If a subject is missing an ordinal scale value but is bracketed by the same values on immediately preceding and subsequent days, the value of the missing day will be imputed to be the same as the immediately preceding and subsequent days. If a subject is missing baseline ordinal scale values from Day 1, baseline values will be set to the Day 2 score. If subjects are missing Day 1 and Day 2, the baseline value will not be imputed. No other data will be imputed.

Clinical Outcome	Score
Death	7
ICU stay with mechanical ventilation	6
ICU stay without mechanical ventilation	5
Non-ICU hospitalization with supplemental oxygen	4
Non-ICU hospitalization without supplemental oxygen	3
Discharge with partial resumption of normal activities	2
Discharge with full resumption of normal activities	1

For use in overall summary statistical presentations, the ordinal categories will be assigned decreasing integer scores, with death a score of 7 and discharge with full resumption of normal activities a score of 1. Frequencies of ordinal scores at each visit will be generated and evaluated by proportional odds ratio analysis, as implemented by logistic regression, including a test of the proportional odds assumption and generation of common odds ratios. For this analysis, the reference response category will be 1= Discharge with full resumption of normal activities with the remaining response categories in numeric sequence to worst (7=Death). Additional exploratory analyses may be conducted to obtain a more complete understanding of the relationship of treatment to the ordinal response.

If it is determined that the level of care provided for particular subjects was driven by factors other than subject disease severity and acuity, data from these subjects will be analyzed in sensitivity analyses. Sensitivity analyses will be generated for ordinal score frequencies, AUC (baseline to Day 7 and to Day 14), post-baseline ordinal scale worsening and days in ICU. These sensitivity analyses will utilize updated ordinal scale measures based on data provided by investigators for subjects who remained in the ICU for reasons other than disease severity (for example, lack of non-ICU beds available). This information will be captured in a spreadsheet that will be locked and signed prior to database lock.

If the conclusions from the primary analysis of the Seven-Level Ordinal Scale differ from those resulting from the above sensitivity analyses, additional exploratory analyses will be performed. These analyses include but are not limited to assessments of whether the analysis conclusions

January 17, 2019

differ only at certain sites or whether the differences in the results remain after adjusting for covariates related to site, disease severity or other factors potentially related to outcome.

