### 3 STUDY ENDPOINTS

#### 3.1 Primary Endpoints

##### 3.1.1 Primary Efficacy Endpoint

The primary efficacy outcome analysis compares Day 7 clinical status ordinal scale scores between treatment groups, and between all VIS410 recipients versus placebo. Clinical status is measured daily for 14 days using the below seven-level ordinal scale, with the classifications presented from the worst clinical outcome (death, score 7) to the best clinical outcome (discharged with full resumption of normal activities, score 1) in descending order; for each day, subject status will be classified by the worst clinical outcome (highest ordinal score) for which they qualify. For subjects who die prior to Day 7, the score of 7 will be carried forward through Day 14.

- Death
- ICU stay with mechanical ventilation
- ICU stay without mechanical ventilation
- Non-ICU hospitalization with supplemental oxygen
- Non-ICU hospitalization without supplemental oxygen
- Discharge with partial resumption of normal activities
- Discharge with full resumption of normal activities

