  - Geographic region of enrollment
- Time to clinical response defined as resolution of at least 4 of 5 vital signs
  - Afebrile with core temperature ≤ 37.8°C, without use of antipyretics (oral ≤ 37.2°C)
  - Oxygen saturation ≥ 95% on room air without support or a return to pre-infection status, if pre-infection status was < 95%
  - Pulse rate ≤ 100/min
  - Systolic blood pressure ≥ 90 mm/Hg, without vasopressor use
  - Respiratory rate ≤ 24 beats per minute
- Clinical status ordinal scale mean area under curve for Days 1-7 and Days 1-14, using linear numeric scores for the ordinal categories.
- Comparison of clinical status ordinal scale scores for selected individual days (ie, Days 3, 4, 5, and 6)
- Comparison of clinical status ordinal scale scores using modified ordinal scale criteria (ie, pooling of selected severity criteria scores)
- Comparison of discrete ordinal scale parameters, including days of ventilator support, days in intensive care, and duration of hospitalization
- Number of days to resumption of usual activities
- All-cause and attributable mortality rates at Day 14, 28 and 56
- Total number of days in hospital and/or intensive care unit (ICU) from admission to discharge and rate of rehospitalization due to influenza A relapse/complication
- The incidence, severity, and duration of signs and symptoms of influenza-like illness as assessed by the FluPRO Questionnaire (see Appendix 16.3.1)
- The percentage of subjects with new bacterial pneumonia/superinfection

January 17, 2019

- The percentage of subjects with influenza-related complications
- VIS410 pharmacokinetic (PK) parameters in serum
- Titer of anti-VIS410 antibody positive samples
- Genotypic and/or phenotypic assessment to determine the emergence of VIS410 and oseltamivir-resistant viruses

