## 4.2 Missing Data Conventions

Partial and missing AE and concomitant medication dates will be imputed with maximum conservatism. If the onset date is missing or partial, the date will be compared as far as possible with the date of first dose of study medication. If no month is present and it is in the same year as the date of first treatment, or the year and month are the same as the first treatment date, the onset date will be imputed as the date of first treatment. Otherwise it will be imputed as 01 January in the available year, or the first day of the month and year available. End dates will be imputed as 31 December in the available year, or the last day of the available month and year collected. Partial dates will be presented in listings, along with classifications of TEAE for AEs or Prior/Concomitant/Both for medications.

Missing data will generally be left as missing, except for partial and missing AE and concomitant medication dates. Special cases, e.g. below the limit of quantification, will be described in the sections that describe the specific parameter's analysis.

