## 9.2 Other Analyses

### 9.2.1 Secondary Endpoints Assessing Ordinal Scale Status

The area under the curve (AUC) over time for a given subject will be calculated (using the linear trapezoidal rule) as the sum of the maximum ordinal score for each day up through Day 7 and Day 14. An analysis of treatment group differences will be performed on these per-subject AUC values using analysis of variance, with treatment group and randomization strata as fixed factors. A sensitivity analysis will be performed that excludes the category of death on study, to determine if death as an outcome skews the results; death as an outcome will also be analyzed as an independent secondary endpoint using all available death information.

A secondary analysis of treatment group effect on the difference in proportions of subjects with the worst (death) versus the best outcome (discharge from hospital and resumption of normal activities) will also be performed. This analysis does not use scores for the ordinal outcome but does account for ordinality and is therefore not dependent on the relationship of score to severity of outcome. P-values will be based on logistic regression treatment comparisons of best vs. worst vs. other categories adjusting for randomization strata.

An exploratory analysis will be performed through an exact categorical analysis of treatment group differences in the ordinal scale results using the worst outcome across all assessments on a per-subject basis.

Additional ordinal scale outcome assessments will include comparison of total numbers of days up to and including Day 14 at more severe scale values (death, time on ventilator, time in ICU) and proportions of subjects with ordinal scale worsening post enrollment.

Using the modified ordinal scale described in Table 2, frequency analyses by visit, AUC analyses (up to Day 7 and up to Day 14) and best versus worst versus other analyses will also be generated.

Proportion outcomes will be analyzed by categorical data analysis methods, including logistic regression adjusted for strata. Additional exploratory subgroup analyses may also be performed, for example, based on various age categories or other subgroup variables. Time from onset of symptoms to study treatment and the number of doses of oseltamivir (Tamiflu) prior to VIS410 treatment for the current case of influenza may be included as covariates in the analyses.

Clinical Outcome	Score
Death	5
ICU stay with mechanical ventilation	4

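### Days after a death on Days 7–13 have no written ordinal score, so the Day 14 AUC is left open for those subjects

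*SAP*

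**What the plan says.** SAP 3.1.1 and 9.1 score clinical status each day from Day 1 to Day 14, from 1 (discharged, full activities) to 7 (death). Both contain the same sentence: "For subjects who die prior to Day 7, the score of 7 will be carried forward through Day 14". SAP 9.1 allows two other imputations: a missing day with equal scores on both sides, and a missing Day 1 taken from Day 2. It then says "No other data will be imputed". SAP 4.2 gives the general default: "Missing data will generally be left as missing, except for partial and missing AE and concomitant medication dates". Protocol 10.5 leaves missing-data handling to the SAP.

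The scale is used well past Day 7. SAP 9.1 asks for category frequencies on every day through Day 14 and a proportional odds analysis at each visit. SAP 3.2 lists as a secondary endpoint the "Clinical status ordinal scale mean area under curve for Days 1-7 and Days 1-14, using linear numeric scores for the ordinal categories". SAP 9.2.1 says the AUC is "calculated (using the linear trapezoidal rule) as the sum of the maximum ordinal score for each day up through Day 7 and Day 14" and repeats it on a five-level modified scale. The same section adds this: "A sensitivity analysis will be performed that excludes the category of death on study".

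On a separate matter, SAP 9.2.5 defines time to usual activities as the first day at VAS 10 minus Day 1, and enters 14 for any subject without a 10 by Day 14. Protocol 6.3.4 collects VAS daily until usual activities are resumed or Day 56. Protocol 10.6.5 states no cap, and SAP 16.1 does not list one among its changes to the protocol.

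**The concern.** The SAP recognises that days after death need a score, but writes the rule only for deaths before Day 7. A death on day d, with d from 7 to 13, leaves 14 − d later days (seven down to one) that the rule does not reach. A Day 14 death leaves none. The other two imputations cannot help: no later score exists to bracket a day after death, and the Day 1 rule is irrelevant. The SAP also does not say how an AUC is formed when days are blank, so two programmers could follow the text and produce different tables.

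The protocol synopsis and protocol 10.1 say that p-values on the primary and secondary endpoints will guide the choice of Phase 3 endpoints. The Day 14 AUC is one of those candidates. How it scores a death should not depend on whether the death falls on Day 6 or Day 7.

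**Working it through.** The plan gives no expected number of deaths and no AUC standard deviation, so it has no figure to reproduce. The check is arithmetic on the SAP 9.1 scores (the protocol synopsis codes the same levels 0 to 6).

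**Inputs.** Level L held constant before death (assumed): ward oxygen 4, ICU without ventilation 5, ICU ventilated 6. Death scores 7 and occurs on day d = 7 to 13.

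**Sum formulas.** Observed days only: L(d − 1) + 7. Death carried to Day 14: the same plus 7(14 − d). Survivor at that level: 14L.

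| Level before death | Survivor | Carried, Day 7 to Day 13 death | Observed only, Day 7 to Day 13 death |
|---|---|---|---|
| Ward oxygen | 56 | 80 to 62 | 31 to 55 |
| ICU, not ventilated | 70 | 86 to 74 | 37 to 67 |
| ICU, ventilated | 84 | 92 to 86 | 43 to 79 |

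All 21 deaths score worse than the same-level survivor if carried, and better if only observed days are summed.

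**The step at Day 7 (ventilated).** Day 6 death, rule applies: 5×6 + 9×7 = 93. Day 7 death, later days blank: 6×6 + 7 = 43. Day 7 death, carried: 43 + 7×7 = 92.

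**Trapezoid.** Observed days give L(d − 2) + (L + 7)/2; a survivor scores 13L. Results are 25.5–49.5 against 52, 31–61 against 65, and 36.5–72.5 against 78, so the ordering is the same. The two formulas named in SAP 9.2.1 are not the same quantity: 14 days at score 6 give 84 by sum and 78 by trapezoid. The protocol synopsis specifies the sum.

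**Five-level scale (death 5; levels 2, 3, 4), observed sum.** Ward: 17–27 against 28 for deaths on Days 7–12, and 29 on Day 13 (no inversion). ICU: 23–41 against 42. Ventilated: 29–53 against 56.

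**Other ways to treat blank days.** Dropping incomplete AUCs removes these deaths from the ANOVA. Averaging observed days, [L(d − 1) + 7]/d, gives no same-level inversion: ventilated 6.08–6.14 against 6.00, ward oxygen 4.23–4.43 against 4.00. Some cross-level inversions remain. A ward-oxygen death on Days 7–10 averages 4.30–4.43 against 5.00 for an ICU survivor, whereas the carried sums are 80–71 against 70.

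**Arm level (40 per arm).** Carrying instead of truncating one Day 8 death moves the arm mean by 7×6/40 = 1.05 points; one Day 13 death moves it by 7×1/40 = 0.175.

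**Other Day 8–14 outputs.** A Day 6 death contributes 9 death-days. A Day 7 death contributes 8 if carried and 1 if later days are blank. With an assumed 2 deaths before Day 7 and 2 on Days 7–13 among 40, the Day 14 ordinal table shows 2/38 = 5.3% dead, against 4/40 = 10.0% mortality.

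**VAS.** A first 10 on Day 14 gives 13 and on Day 15 gives 14. Day 20 should give 19 and Day 56 should give 55, but both are entered as 14, as are non-recoverers and deaths without an earlier 10. If recovery times were exponential with medians of 10.5 to 42 days (assumed), the share entered as 14 would be 2^(−14/median), or 39.7% to 79.4%. Once more than half are entered as 14, the summary median is the cap itself.

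**The case against.** The strongest reply is that there is no gap. SAP 3.1.1 says that each day "subject status will be classified by the worst clinical outcome (highest ordinal score) for which they qualify", and a dead subject qualifies for Death on every later day. Those days would then be classified rather than imputed. SAP 9.2.1 supports this by comparing "total numbers of days up to and including Day 14 at more severe scale values (death, time on ventilator, time in ICU"), since counting days at Death presumes that Death persists. SAP 9.2.7 also derives all-cause mortality partly from the ordinal-scale form. This reading is plausible and may well be the intent. It does not close the matter, because it makes the written carry-forward rule unnecessary. Whether sites enter Death daily also depends on form instructions that the documents do not contain.

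The reach is narrow, and that stands. The clearly exposed named endpoint is the Day 1–14 AUC on its two scales. The individual-day comparison names only Days 3–6. The trial is exploratory and unpowered (SAP 2.2), and p-values are informational (SAP 4.1). The same-level inversions also need a missing-day rule that the SAP does not state.

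A reader might infer more than the text supports:

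- That the primary analysis mishandles death. It does not: earlier deaths are carried, and a Day 7 death scores 7 on its own day.
- That late deaths are hidden. Mortality is analysed separately at Days 14, 28 and 56, and worst outcome per subject still captures them.
- That a late death generally beats recovery. Against an assumed recovering survivor (5×4 + 2×3 + 4×2 + 3×1 = 37), only two of the 21 truncated sums are lower (31 and 35) and one ties.
- That treatment comparisons are biased in a known direction. Nothing in the documents allows that to be worked out.

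On VAS, the rule is explicit, the days-to-resumption output is descriptive, and a 14-day ceiling matches the FluPRO duration rule in SAP 9.2.6. What remains is an undeclared truncation of data that are collected.

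**Conclusion.** The point holds as a gap in the written rule that should be fixed. Followed literally, SAP 3.1.1 and 9.1 leave days after a Day 7–13 death unscored, and nothing else in either document clearly supplies a score. For one subject the consequence can be large: 43 against 92 for a ventilated Day 7 death, depending on whether observed days are summed or death is carried. These figures assume a constant level before death. The effect on treatment comparisons cannot be computed, because the number of deaths on Days 7–13 and the AUC standard deviation are not given. Confidence is medium, since daily scoring of Death by sites would remove the problem in practice. The VAS cap is a separate, minor point.

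**What to change.** 1. In SAP 3.1.1 and 9.1, change the trigger from death before Day 7 to death on or before Day 14. Carry 7 (5 on the modified scale) from the day of death through Day 14 in all ordinal outputs, except the AUC sensitivity analysis that excludes death.
2. In SAP 9.2.1, keep one AUC formula, the protocol's sum of daily scores, and delete the reference to the trapezoidal rule.
3. Separately, in SAP 9.2.5, summarise time to usual activities through Day 56 by Kaplan-Meier or cumulative incidence, keeping deaths as never resuming. At the least, list the cap in SAP 16.1 as a change from the protocol and report how many subjects in each arm were assigned 14.

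The cost is SAP wording and minor reprogramming before database lock. No new data are needed.

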- ¹³ Additional targeted physical exam may be performed throughout the study as needed at the Investigator's or his/her designee's discretion.
- ¹⁴ The Influenza Patient Reported Outcomes (FluPRO) Questionnaire (Appendix 14.1) must be completed (ie, self-reported) by the subject at baseline (Day 1) and daily thereafter through Day 14. Subjects who are not able to complete the questionnaire at baseline (Day 1) will be exempt from this assessment throughout the study. The FluPRO will be completed at home for subjects that are discharged from the hospital prior to Day 14.
- ¹⁵ The ordinal scale will be completed from baseline (Day 1) and daily thereafter through Day 14. For each day, subjects will be classified by the worst clinical outcome for which they qualify.
- ¹⁶ A urine or serum pregnancy test must be performed at screening locally (ie, by the investigative site) within 2 days prior to dosing. Negative results must be obtained prior to randomization.
- ¹⁷ A serum pregnancy test will be performed at the central lab for all female subjects of childbearing potential following randomization at baseline
- ¹⁸ Subjects to be enrolled based on the Investigator's discretion including any local laboratory results per SOC at institution.
- ¹⁹ See Laboratory Assessments for list of tests to be performed by the Central Lab in Appendix 14.2.
- ²⁰ Serum creatinine to be done locally within 24 hours prior to randomization, the result is required for oseltamivir dosing.
- ^{20a} ESR to be performed locally.
- ²¹ A chest x-ray or computed tomography (CT) scan taken per SOC within 72 hours before dosing is acceptable.
- ²² Healthcare utilization (total length of hospital stay, length of ICU stay, and rehospitalization) will be captured through the last follow-up visit.
- ²³ If the subject has any history of delayed gastric emptying, including premenstruation syndrome or menstruation, he or she may receive oral premedications 120 minutes prior to IV VIS410/placebo infusion.
- ²⁴ VIS410/placebo will be administered over 2 hours. Infusion time can be extended to up to 4 hours at discretion of the Investigator only if local infusion site-related symptoms occur.

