8.3.2 Day of Treatment Procedures (Day 1)

On Day 1, eligibility of the subjects will be confirmed and assessments will be performed as described in Table 1.

All results from the screening procedures required to evaluate eligibility must be available prior to randomization on Day 1. Any abnormal assessment at the screening will be assessed according to its clinical relevance, and if found relevant, the subject will not be included in the study.

Once a subject has fulfilled the entry criteria, he/she will be assigned a unique identifier. The site's unblinded pharmacist or properly trained designee will randomize the subject using the IWRS.

On Day 1, all subjects will receive the pretreatment regimen prior to receiving VIS410/placebo.

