## 4 GENERAL ANALYSIS DEFINITION

### 4.1 General Considerations

All statistical analyses and summary information are to be generated according to this SAP. Any deviations from this SAP will be documented in the clinical study report (CSR).

These descriptive statistics will be presented for continuous parameters: the number of subjects used in the calculation (n), mean, standard deviation (SD), median, minimum, and maximum values. For PK parameters, the geometric mean and coefficient of variance (CV) will also be presented. All continuous summaries will display the minimum and maximum value with the same number of decimals collected in the data. The median, mean, geometric mean and CV will display 1 additional decimal, and the SD and SE will display 2 additional decimals. For categorical variables, frequencies and percentages will be reported. All percentages will be reported to 1 decimal; all p-values will be reported to 3 decimals.

All temperature measurements will be presented as degrees Celsius. Degrees in Fahrenheit will be converted with this formula:

$$T_C = (T_F - 32) * (5/9),$$

where  $T_C$  is a Celsius temperature and  $T_F$  is a Fahrenheit measurement.

Since this is a phase 2 study rigorous control over type 1 error will not be used; all statistical comparisons will be performed using 2-sided tests at the 0.05 significance level, unless specifically stated otherwise. All null hypotheses will be defined as no treatment difference. All p-values are presented for informational purposes only; there will not be any adjustments for multiple comparisons.

All analyses, summary tables, figures, and data listings will be generated with SAS version 9.4 or higher. Specialized PK software will be used for some PK analyses.

Baseline is defined as the latest non-missing measurement taken prior to study drug administration.

January 17, 2019

All summaries will be by actual visit, no visit windows for analysis will be defined. In general, summaries will be by treatment groups, and will include a combined VIS410 treatment group, in addition to the individual low dose (2000 mg) VIS410, high dose (4000 mg) VIS410, and Placebo treatment groups, unless specified differently. Summaries of disposition, other baseline data, and adverse events will also include an overall column.

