### **9.2.8 Nasopharyngeal Viral Load**

Standard non-compartmental approaches using Phoenix WinNonlin (Certara, Princeton, NJ, USA; Version 7.0 or higher) will be used to calculate nasopharyngeal viral load (VL) parameters. Viral load at each study visit, proportion of subjects with negative results at each study visit, peak VL, and VL AUC based on qRT-PCR and TCID50 from nasopharyngeal secretions will be summarized with n, mean, SD, geometric mean, CV, minimum and maximum values in the MITT population overall and per influenza A virus subtype. All available viral data within the MITT population will be assessed to calculate proportion of subjects with negative results at each study visit. For all other calculated parameters, viral load will be assessed on all samples in the MITT population collected through Day 7 for TCID50 and Day 14 for qRT-PCR.

January 17, 2019

Viral shedding by qRT-PCR or TCID50 versus time and VL AUC will be assessed using baseline-adjusted and non-adjusted comparisons. Each of the analyses described above will also be performed for the MITT subgroup comprised of all MITT subjects with a positive baseline-positive influenza viral culture result. In addition, VL and VL AUC by qRT-PCR for the first 50 subjects will be listed through Day 28 if subject is qRT-PCR positive on Day 14 and the Day 28 sample is tested by qRT-PCR (no summary statistics will be presented). For missing data on Day 1 post-dose, Day 3, Day 5 and Day 7, the analysis will be conducted without imputation and with the last observable measurement carried forward (LOCF). For missing data on Day 1 predose, the analysis will be conducted by replacing the missing data with the Day 1 postdose observable measurement. Subjects missing both Day 1 predose and Day 1 postdose will be removed from the analysis. Some parameters will also be analyzed using baseline-adjusted values. Viral load data will be normalized by dividing the value by the baseline value.

ANOVA will be used to assess the difference between treatment groups in the VL AUC from nasopharyngeal swabs based on qRT-PCR and TCID50. If the assumptions needed for ANOVA are not met, log transformation and/or non-parametric methods will be used. Differences between groups in peak post-baseline VL (qRT-PCR and TCID50) will be tested, and the proportion of subjects with peak VL (by qRT-PCR and TCID50) occurring post-baseline.

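### A missing Day 1 ordinal score is filled with the post-infusion Day 2 score, so the post-enrolment worsening comparison can misclassify affected subjects in either direction

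*SAP*

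**What the plan says.** SAP section 4.1 gives one definition of baseline for the whole analysis: "Baseline is defined as the latest non-missing measurement taken prior to study drug administration". Section 4.2 sets the default for gaps: "Missing data will generally be left as missing, except for partial and missing AE and concomitant medication dates". It adds that special cases are described in the section for the parameter concerned.

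Section 9.1 contains such a special case for the seven-level ordinal scale: "If a subject is missing baseline ordinal scale values from Day 1, baseline values will be set to the Day 2 score". If both days are missing, no baseline is imputed. For a gap on a later day, section 9.1 imputes only when the days immediately before and after carry the same score.

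The timing comes from the protocol. Section 8.3.2 places dosing on the first day: "On Day 1, all subjects will receive the pretreatment regimen prior to receiving VIS410/placebo". Table 1, footnote 15, gives the scoring schedule: "The ordinal scale will be completed from baseline (Day 1) and daily thereafter through Day 14".

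The baseline score is used in SAP section 9.2.1, which compares "proportions of subjects with ordinal scale worsening post enrollment". Section 9.1 also plans to repeat that assessment as a sensitivity check, alongside the score frequencies, the ordinal AUCs and the count of ICU days. The Day 1 score also enters the daily frequency tables and the ordinal AUCs.

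For nasopharyngeal viral load, section 9.2.8 handles a missing predose value in a related way: "the analysis will be conducted by replacing the missing data with the Day 1 postdose observable measurement".

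**The concern.** A post-treatment value used as a baseline can already carry an effect of treatment or of early disease progression. When the outcome is change from that baseline, whatever happened in the first day is removed from the comparison. Worsening after enrolment is a planned between-arm comparison. The SAP says that p-values from this trial help to choose endpoints for Phase 3, so the classification behind each one should be sound.

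The rule can also yield baselines that the trial population should not have. Inclusion criterion 4 requires oxygen support, so the expected Day 1 score is 4, 5 or 6. A subject off oxygen in a non-ICU bed on Day 2 would be given a baseline of 3, and a subject who died on Day 2 a baseline of 7.

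**Working it through.** No sample size, power or alpha figure in the plan depends on this rule, so there is no stated figure to reproduce. The check is to apply the rule to possible score paths.

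**Inputs**
- Expected true Day 1 score, d1: 4, 5 or 6 (protocol section 5.2.1, criterion 4, with the scores in SAP section 9.1).
- Day 2 score, d2: 1 to 7.
- Worst score after Day 2, m: 1 to 7. A death stays at 7 (SAP section 9.1).
- Arm size: 40 (SAP section 2.1).
- Assumption: worsening means any later score above baseline. The SAP does not define it further.

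**Classification**
- True worsening: max(d2, m) > d1.
- Worsening under the rule: m > d2, because the Day 1 to Day 2 change is fixed at zero.
- Hidden worsening: d2 > d1 and m ≤ d2.
- False worsening: d2 < m ≤ d1.

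**Pattern counts.** For each d1 there are 6 × 7 = 42 patterns with d2 from 1 to 6, plus 1 with d2 = 7, giving 43. Over three values of d1 that is 129.
- Hidden: d1 = 4 gives 5 + 6 + 1 = 12; d1 = 5 gives 6 + 1 = 7; d1 = 6 gives 1. Total 20.
- False: d1 = 4 gives 6; d1 = 5 gives 10; d1 = 6 gives 15. Total 31.

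These count patterns and are not probabilities. They show that both errors occur, not which is more common.

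**Worked paths, Days 1 to 7**

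| True path | Baseline under rule | Truly worsened | Worsened under rule | AUC, trapezoid: true / rule | Sum of scores: true / rule |
|---|---|---|---|---|---|
| 4,5,5,5,4,4,3 | 5 | yes | no | 26.5 / 27.0 | 30 / 31 |
| 4,3,3,4,4,3,3 | 3 | no | yes | 20.5 / 20.0 | 24 / 23 |

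Section 9.2.1 describes the AUC both as a trapezoidal area and as a sum of daily scores, so both are shown. The trapezoidal AUC moves by half of d2 − d1, and the sum by the whole of it. A one-level difference therefore shifts them by 0.5 and 1.

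**Death on Day 2 with Day 1 missing.** Baseline is 7 and every later score is 7. Since 7 > 7 is false, the subject counts as not worsened.

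**Effect on an arm's proportion.** One misclassified subject moves it by 1/40 = 2.5 percentage points. The number of missing Day 1 scores is not given. If 1, 2 or 4 subjects in one arm are affected and all are misclassified in the same direction, the shift is 2.5, 5.0 or 10.0 points. These are upper bounds under that assumption.

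**The case against.** The strongest defence is that this is a declared special case. SAP section 4.2 allows parameter-specific rules. Protocol section 10.5 leaves missing-data methods to the SAP and names last observation carried forward and interpolation only as possibilities. A specific fallback beside a general definition leaves the programmer in no doubt. That stands as far as it goes: the rule is workable and prespecified. It still replaces a pre-dose baseline with a post-dose one without saying so, and permission to have a special rule does not make this one suitable for a change-from-baseline outcome.

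Second, an observed Day 1 score is the worst status for the whole day, and dosing falls on that day, so it may include hours after the infusion. That is correct, and the contrast between pre-dose and post-dose is less sharp than section 4.1 suggests. It does not justify moving a further day past treatment.

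Third, the entry level cannot always be rebuilt. Protocol section 10.2 counts CPAP and BiPAP as positive pressure ventilation, so the randomisation stratum does not map directly to the ICU-with-ventilation level. Protocol section 6.3.5 lists ICU dates, not times. Ventilation start and stop times are recorded (section 6.3.3). Reconstruction will work for some subjects only.

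A reader might infer three stronger things that the documents do not support:
- **That the primary result is biased.** The Day 7 proportional odds model in section 9.1 names no baseline-score covariate, so imputing Day 1 does not alter that comparison.
- **That the rule systematically hides harm or favours VIS410.** The error runs both ways, and nothing shows that missing Day 1 scores would differ by arm.
- **That the viral-load rule is an equal fault.** That substitute is a swab taken up to 2 hours after administration (Table 1, footnote 26), not a next-day status. Section 9.2.8 plans unadjusted as well as baseline-adjusted comparisons. The case there is much weaker.

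**Conclusion.** The point holds as a minor one. Section 9.1 departs from the pre-dose baseline of section 4.1 without acknowledging it, and the substitution is unsuitable for the comparison of worsening after enrolment, where it can produce both missed and false worsening. It can also put values below 4, or a death, into the Day 1 frequencies of a population that required oxygen at entry, if the imputed baseline is tabulated as Day 1.

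The size is 2.5 points on an arm's worsening proportion per misclassified subject, assuming 40 per arm and the definition of worsening used above. The total depends on a count the documents do not give. It may well be small, since subjects are in hospital on Day 1. The effect on ordinal AUC is slight, and the study is exploratory, with p-values presented for information only.

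**What to change.** Amend SAP section 9.1 as follows.

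1. For the worsening analysis and the Day 1 frequencies, rebuild a missing Day 1 score from entry records where they allow it: oxygen status at entry, ventilation start and stop times, ICU dates and positive pressure ventilation status. Record the result in a spreadsheet signed and locked before database lock, as sections 9.1 and 9.2.3 already do for ICU stays unrelated to severity and for historic oxygen saturation. Where the score cannot be rebuilt, leave it missing.
2. Keep the Day 2 substitution for ordinal AUC when Day 1 cannot be rebuilt, because leaving Day 1 missing there would lose or shorten the subject's AUC. Otherwise use it only as a labelled sensitivity analysis.
3. Report the number of Day 1 scores rebuilt, substituted and left missing in each arm, and state in section 9.1 how the rule relates to section 4.1.
4. In section 9.2.8, add a check of the baseline-adjusted viral-load comparisons that excludes subjects whose predose value was replaced by the postdose one.

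The cost is SAP wording, a short blinded data review and one extra viral-load run. The downside is that a few subjects may drop out of the worsening analysis.
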